11.0 Ethical Considerations

This study is to be conducted according to US and international standards of Good Clinical Practice (FDA Title 21 part 312 and International Conference on Harmonization guidelines), applicable government regulations and Institutional research policies and procedures.

This protocol and any amendments will be submitted to a properly constituted independent Institutional Review Board (IRB), in agreement with local legal prescriptions, for formal approval of the study conduct. The decision of the IRB concerning the conduct of the study will be made in writing to the investigator before commencement of this study.

All subjects for this study will be provided a consent form that is compliant with local and federal regulations, describing this study and providing sufficient information for subjects to make an informed decision about their participation in this study. See Attachment for a copy of the Subject Informed Consent Form. This consent form will be submitted with the protocol for review and approval by the IRB for the study. The formal consent of a subject, using the IRB-approved consent form, must be obtained before that subject is submitted to any study procedure.

This consent form must be signed by the subject or legally acceptable surrogate, and the investigator-designated research professional obtaining the consent.

12.0 STUDY FINANCES

12.1 Funding Source

This study is funded by Millennium.

12.2 Conflict of Interest

Any investigator who has a conflict of interest with this study (patent ownership, royalties, or financial gain greater than the minimum allowable by their institution, etc.) must have the conflict reviewed by a properly constituted Conflict of Interest Committee with a Committee-sanctioned conflict management plan that has been reviewed and approved by the study sponsor prior to participation in this study. All Jefferson University Investigators will follow the TJU Conflicts of Interest Policy for Employees (107.03).

12.3 Subject stipends or Payments

There are no subject stipends or payments.

13.0 Publication Plan

Any formal presentation or publication of data from this trial may be published after review and comment by Millennium and prior to any outside submission. Millennium must receive copies of any intended communication in advance of publication (at least fifteen working days for presentational materials and abstracts and thirty working days for manuscripts). These requirements acknowledge Millennium's responsibility to provide peer input regarding the scientific content and conclusions of such publications or presentations. Principal Investigation/Institution shall have the final authority to determine the scope and content of its publications, provided such authority shall be exercised with reasonable regard for the interests of Millennium and, in accord with the trial contract and shall not permit disclosure of Millennium confidential or proprietary information.

Neither the complete nor any part of the results of the study carried out under this protocol, nor any of the information provided by the sponsor for the purposes of performing the study, will be published or passed on to any third party without the consent of the study sponsor. Any investigator involved with this study is obligated to provide the sponsor with complete test results and all data derived from the study.

15.0 Appendices

Appendix I ECOG Performance status scale

Appendix II Visit Schedule

Appendix III SAE form

Appendix IV MMSE

Appendix V QoL forms

Appendix VI Case Report Forms

Appendix I: ECOG Performance Status

Grade	Descriptions
0	Normal activity. Fully active, able to carry on all pre-disease performance without restriction.
1	Symptoms, but ambulatory. Restricted in physically strenuous activity, but ambulatory and able to carry out work of a light or sedentary nature (e.g., light housework, office work).
2	In bed <50% of the time. Ambulatory and capable of all self-care, but unable to carry out any work activities. Up and about more than 50% of waking hours.
3	In bed >50% of the time. Capable of only limited self-care, confined to bed or chair more than 50% of waking hours.
4	100% bedridden. Completely disabled. Cannot carry on any self-care. Totally confined to bed or chair.
5	Dead

Appendix II: Visit Schedule

	Prior to Registration	Pre-treatment	Concurrent phase		Observation phase	Maintenance phase	Recommended Follow up
Time (day)	-14 to -1	-30 to -1	1-7	8-14	Day 13-42	From Day 43 to 1 year	Year 2 and onwards
Informed consent	X						
Demographics	X						
Medical history	X	X					
H & P	X	X	X ⁷	X ⁷	X ⁵	Q 2 months	X ⁶
Neuro exam	X	X	X ⁸	X ⁷	X ⁵	Q 2 months	X ⁶
MMSE		X			X ⁵	Q 2 months	X ⁶
QoL		X			X ⁵	Q 2 months	X ⁶
Vitals		X	X ⁷	X ⁷	X ⁵	Q 2 months	X ⁶
Weight		X	X ⁷	X ⁷	X ⁵	Q 2 months	X ⁶
KP/ECOG	X	X	X	X ⁷	X ⁵	Q 2 months	X ⁶
CBC w diff	X	X	X ⁷	X ⁷	X ⁵	Weekly ³	X ⁶
CMP, Mg +	X	X	X ⁸	X ⁷	X ⁵	Q 2 months	X ⁶
PT/PTT/INR		X					
Lipid Panel			X ⁷	X ⁷	X ⁵	Q 2 months	
EKG		X					
b-HCG	X ⁹						
MRI Brain		X			X ¹	Q 2 months	X ⁶
Treatment:							
RT			X ²	X ²			
MLN8237			X ³	X ³		X ⁴	

Q = every

H & P = History & Physical

NOTE:

1. Brain MRI should be done between days 35-42, then every 2 months for 1st year.
2. RT: daily on weekdays for a total of 10 treatments.
3. Alisertib: BID on days of RT only.
4. Alisertib: 50 mg BID on days 1-7 every 21 days, for up to 18 cycles or until progression.
5. Between day 39 to day 45 (at the end of 30 day observation period), then every 2 months
6. Every 3 months from year 1 to year 2, then every 4-6 months afterwards.
7. All items only need to be done at least once during week 1 and at least once during week 2.
8. Until discontinuation of Alisertib.
9. Pregnancy test should be done within 7 days prior to registration, if applicable

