1.1 Specific Aims and Hypothesis

1.1.1 Hypothesis

Malignant gliomas are the most common primary brain tumors in adults ^[1]. The standard of care for newly diagnosed high grade glioma, especially glioblastoma multiforme (GBM), is maximal surgical resection, followed by radiation treatment (RT) and concurrent and adjuvant chemotherapy with temozolamide (TMZ) ^[2]. Nonetheless, 90% of the patients recur within 2 years ^[2, 3]. There is no standard treatment for recurrent high grade glioma. Therapeutic options include repeat surgery, re-irradiation, cytotoxic agents, and target therapies. Fractionated stereotactic radiotherapy (FSRT) may offer some improvement in survival with minimal toxicity for patients with previously treated gliomas. Our institution published one of the largest single institution experiences of using FSRT in recurrent high grade glioma. The treatment is well tolerated with a favorable median survival of 11 months after FSRT. Aurora kinase A is overexpressed in many malignant tumors ^[4]. Overexpression of Aurora-A has a prognostic value in high grade glioma. Administration of Aurora-A kinase inhibitor can suppress the growth of GBM, as well as be synergistic to radiation treatment ^[5-8]. Alisertib (MLN8237) is a potent second generation Aurora-A kinase inhibitor ^[4, 9, 10]. Combining FSRT with Alisertib for patients with recurrent high glioma likely would result in improved local control and prolonged survival. The effect of combination therapy may be more than additive effect, as suggested by a preclinical study ^[7]. The current phase I study will assess the safety profile of combining different doses of Alisertib with FSRT. We will determine the MTD (maximum tolerated dose), as well as a recommended phase II trial dose of Alisertib when used concurrently with radiation treatment for recurrent glioma patients.

1.1.2 Primary Aims:

- Evaluate the safety and tolerability of the study treatment
- To determine the Maximum Tolerated Dose (MTD) of Alisertib when combined with fractionated stereotactic radiation treatment for recurrent high grade glioma.

1.1.3 Secondary Aims:

- To estimate 6 month progression free survival rate
- To estimate the median time to progression
- To estimate overall survival
- To estimate the impact on quality of life (QoL)

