Clinical pharmacokinetic data available as of 20 April 2012 are summarized in Section 5.2 of the IB. Upon oral administration of PIC formulation to patients with advanced nonhematologic malignancies, absorption of Alisertib was fast, with peak plasma concentrations generally achieved by 2 hours post-dose. Negligible urinary excretion of Alisertib was observed in humans. The renal clearance of Alisertib in humans was less than 0.1% of apparent oral clearance. Steady-state plasma exposures of Alisertib increased in an approximately dose-proportional manner over the range of 5 to 200 mg/day in patients with advanced solid tumors. Overall mean steady-state terminal half-life following multiple-dose administration in patients with nonhematologic malignancies was approximately 22 hours. The overall mean peak/trough ratios were 2.6 and 5.0 for BID and QD dosing, respectively. The overall mean accumulation ratios were 2.8 and 1.9 for BID and QD dosing, respectively. Pharmacokinetic steady-state conditions were approximately achieved by Day 7 following daily oral administration.

Based on the results of a population PK analysis in 294 adult cancer patients, the apparent oral clearance of MLN8237 CL/F was unaffected by age, body weight, BSA, or the UGT1A1 genotype (number of *28 alleles). These results support the use of a common fixed starting dose of MLN8237 independent of UGT1A1 genotype status, age or body size in the adult patient population, in the ongoing and planned clinical trials.

Results from the relative BA study in 14 patients indicated that systemic exposures achieved following administration of the enteric-coated-tablet (ECT) and powder-in-capsule (PIC) formulations of MLN8237 are generally similar, based on relative BA of ECT in reference to PIC of approximately 90% (90% confidence interval: 74.4%-108.8%), supporting transition from the PIC to ECT in clinical development.

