Alisertib is structurally related to the benzodiazepines (BZD) (e.g., diazepam, lorazepam) and also has activity against the GABA α 1 BZD receptor. BZD-like effects (e.g., somnolence, confusion, memory loss) have been observed to be associated with the onset of maximal plasma concentration (e.g., T_{max} [time to maximum plasma concentration]). CNS effects associated with peak plasma levels have been generally managed by administration of divided doses (e.g., BID administration), although dose reductions have sometimes been required. While CNS effects attributed to Alisertib were also generally reversible and manageable by dose delay or reduction, the causal relationship, and thus optimal approach to management, were sometimes confounded by diverse causes including, but not limited to, concomitant medications (e.g., narcotic analgesics, antianxiety medications), comorbidities (e.g., infection, anemia, electrolyte abnormalities), and progressive malignancy (e.g., brain metastases).

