6.5 Quality of Life Measurement

The validated EORTC core quality of life questionnaire (QLQ-C30, version 3.0) supplemented by a brain cancer specific health-related quality of life questionnaire, QLQ-BN20, will be administered according to trial calendar. (Appendix V)

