29. How would you rate your overall health during the past week?

1 2 3 4 5 6 7

Very poor

Excellent

30. How would you rate your overall quality of life during the past week?

1 2 3 4 5 6 7

Very poor

Excellent

EORTC OLO - BN20

Patients sometimes report that they have the following symptoms. Please indicate the extent to which you have experienced these symptoms or problems during the past week.

During the past week:	Not at All	A Little	Quite a Bit	Very Much
31. Did you feel uncertain about the future?	1	2	3	4
32. Did you feel you had setbacks in your condition?	1	2	3	4
33. Were you concerned about disruption of family life?	1	2	3	4
34. Did you have headaches?	1	2	3	4
35. Did your outlook on the future worsen?	1	2	3	4
36. Did you have double vision?	1	2	3	4
37. Was your vision blurred?	1	2	3	4
38. Did you have difficulty reading because of your vision?	1	2	3	4
39. Did you have seizures?	1	2	3	4
40. Did you have weakness on one side of your body?	1	2	3	4
41. Did you have trouble finding the right words to express yourself?	1	2	3	4
42. Did you have difficulty speaking?	1	2	3	4
43. Did you have trouble communicating your thoughts?	1	2	3	4
44. Did you feel drowsy during the daytime?	1	2	3	4
45. Did you have trouble with your coordination?	1	2	3	4
46. Did hair loss bother you?	1	2	3	4
47. Did itching of your skin bother you?	1	2	3	4
48. Did you have weakness of both legs?	1	2	3	4
49. Did you feel unsteady on your feet?	1	2	3	4
50. Did you have trouble controlling your bladder?	1	2	3	4

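### No quality-of-life form covers the two weeks of concurrent FSRT and alisertib, so the acute QoL effect of that course goes unmeasured and is likely to be understated

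*Combined protocol and SAP*

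**What the plan says.** Section 1.1.3 lists the impact on QoL as a secondary aim, and sections 2.2 and 3.3 repeat it. Section 6.5 names the instruments, QLQ-C30 version 3.0 and QLQ-BN20, and says only that they "will be administered according to trial calendar". Section 7.2 describes no QoL analysis, so Appendix II alone fixes when QoL is observed.

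In Appendix II the QoL row has an entry at pre-treatment (days -30 to -1), none for days 1-7, none for days 8-14, and then an entry in the observation phase carrying note 5: "Between day 39 to day 45 (at the end of 30 day observation period), then every 2 months". After that it is 2-monthly in maintenance and less often from year 2. Other rows, such as history and physical, vitals, weight and blood count, do have entries in both concurrent weeks. These carry note 7: "All items only need to be done at least once during week 1 and at least once during week 2".

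In Appendix V, QLQ-C30 items 6-30 refer to the past week, and QLQ-BN20 opens with "Please indicate the extent to which you have experienced these symptoms or problems during the past week". QLQ-C30 items 1-5 state no recall period and describe the patient's condition when the form is completed.

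On treatment, sections 5.2 and 6.3 give alisertib on the 10 radiation days at the cohort's level (10 to 50 mg BID). In maintenance every patient starts at the same dose, taken on days 1-7 of each 21-day cycle.

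**The concern.** The concurrent course is what this phase I trial tests, and it is where the cohorts differ by design. Section 1.6 lists sedation, confusion, nausea, mucositis and fatigue among the drug's risks. QLQ-C30 and QLQ-BN20 ask about nausea, tiredness, concentration, daytime drowsiness and unsteadiness, so the instruments suit the expected effects, but they are given only before and well after the exposure.

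Section 1.6 expects the toxicities to reverse, and section 1.5 says of the CNS effects: "While CNS effects attributed to Alisertib were also generally reversible and manageable by dose delay or reduction". Section 1.4.2 adds: "Overall mean steady-state terminal half-life following multiple-dose administration in patients with nonhematologic malignancies was approximately 22 hours". A patient who felt unwell in weeks 1 and 2 and recovered by week 5 would show no change from baseline on the first form. A schedule followed exactly could then report a mild QoL effect of the combination because nobody was asked at the time. These data cannot be recovered afterwards.

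**Working it through.** **1. The plan's own calendar.** The observation phase runs from day 13 to day 42: 42 − 13 + 1 = 30 days, matching the stated 30-day period. It implies a last fraction on day 12.

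**2. End of the concurrent course.** Ten weekday fractions with no interruption (Appendix II note 2, section 1.3.1) end on day 12 for a Monday start and on day 14 for any other weekday start.

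**3. Gap to the first post-baseline form (days 39-45).**
- Monday start: 39 − 12 = 27 to 45 − 12 = 33 days.
- Other start: 39 − 14 = 25 to 45 − 14 = 31 days.
- Overall: 25 to 33 days.

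**4. Concurrent days recalled.** Taking the past week as the 7 days before the form, the earliest recalled day is 39 − 7 = 32. The course ended 18 to 20 days before that, so 0 of 10 treatment days are recalled. Interruptions do not change this. Seven missed treatment days, the most that section 1.3.1 classes as acceptable, stretch the course to 17 weekdays. These end on day 23 for a Monday to Thursday start and on day 25 for a Friday start, still before day 32.

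**5. Drug exposure by then.** From day 14 to day 32 is 18 × 24 = 432 hours, and 432 / 22 ≈ 20 half-lives. This describes plasma level, not recovery of symptoms.

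**6. What a week-2 form would recall.** Any seven consecutive days contain five weekdays. A form on day 12 (Monday start) recalls days 5-11, of which days 5, 8, 9, 10 and 11 are treatment days: 5, against 0 now. Counting the form day itself gives days 6-12 and again 5.

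**7. Maintenance forms.** Cycle day = (visit day − maintenance start day) mod 21 + 1. Dosing days recalled = how many of the 7 days before the form are cycle days 1-7. Assumptions: maintenance starts on day 43, and 2 months means 60 or 61 days.

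| First form | Interval | Delay | Dosing days recalled, five first-year maintenance forms |
|---|---|---|---|
| Day 42 | 61 days | none | 0, 0, 0, 2, 4 |
| Day 45 | 61 days | none | 0, 0, 0, 0, 1 |
| Day 39 | 61 days | none | 0, 1, 3, 5, 7 |
| Day 39 | 60 days | none | 0, 3, 6, 5, 2 |
| Day 42 | 61 days | one week, before the first maintenance form | 3, 5, 7, 5, 3 |

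The last row uses a one-week delay of the kind section 6.4 provides for. Example: visit day 42 + 61 = 103 gives cycle day (103 − 43) mod 21 + 1 = 19. The delay makes it 12, whose recall week (cycle days 5-11) holds 3 dosing days. The count therefore ranges from 0 to 7 of 7. If the cycle phase were random, forms on cycle days 2 to 14 would recall at least one dosing day: 13 of 21.

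**The case against.** **The objective is not confined to acute effects.** This stands. A reader might infer that the QoL objective cannot see the treatment's impact at all, but the documents do not support that. Baseline against days 39-45, and the later forms, can show lasting or cumulative effects, disease control, and toxicity that arises off drug. Section 1.5 itself reports myelosuppression in the treatment-free period.

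**The understatement is not proven.** This stands in part. Half-life is not symptom recovery, and the statement on reversible CNS effects gives no time course. It cannot be claimed that the trial would report no impact whatever the truth. That none of the 10 concurrent days is recalled does not depend on this assumption.

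**Acute toxicity is recorded elsewhere.** Section 8.2 requires questioning about adverse events at each contact, section 6.2 grades toxicity by CTCAE, and Appendix II schedules physical and neurological examinations in both concurrent weeks. That protects the safety objective. It is clinician grading, and does not replace the patient-reported outcome the QoL objective names.

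**Note 7 might be read to include QoL.** It speaks of all items, but the QoL cells for weeks 1 and 2 are empty and carry no note 7 mark.

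**Maintenance forms are not systematically off-drug.** This stands. A reader might infer from one worked calendar that they mostly describe drug-free weeks. The pattern changes with the first form's date, the interval and a single delay. Dosing also occupies only 7 of 21 days, so a representative sample of maintenance time would be two-thirds off drug.

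**No QoL comparison between dose levels is planned.** This also stands. With 3 to 6 patients per level it would say little even with week-2 forms, so the loss of such a comparison is not part of this point.

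**Conclusion.** The point holds for the concurrent phase. No QoL form recalls any of the 10 treatment days, and the first post-baseline form comes 25 to 33 days after the last fraction. The gap assumes an uninterrupted course; the zero count survives interruptions of up to seven treatment days. The acute QoL impact of the combination therefore goes unmeasured. That it is likely to be understated rests on the further assumption, consistent with sections 1.5 and 1.6, that much of the acute effect has eased by days 32 to 45.

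For maintenance the finding is narrower: the forms are unanchored to the cycle, and what they recall is left to the calendar.

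This concerns a secondary, descriptive objective in up to 24 patients. It does not touch dose escalation or the MTD. It is worth changing because the remedy is cheap and the missing data cannot be collected later.

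**What to change.** In Appendix II, add QoL to the days 8-14 column, at the week-2 visit already required under note 7 and ideally on the last radiation days. MMSE can be added there if wanted. In section 6.5, state that this form is the concurrent-phase QoL assessment. The cost is one extra self-completed form of 30 + 20 = 50 items per patient, at most 24 forms in all, with no new visit.

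For maintenance, record the cycle day, or the date of the last alisertib dose, with each form, so that results can be read as on-drug or off-drug weeks. Do the same for the first post-baseline form: its window runs to day 45 while maintenance may start on day 43, so a form on day 44 or 45 could recall one or two maintenance dosing days.

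Moving all maintenance forms to a fixed cycle day is an optional choice of target, not a correction. A form on cycle day 8 would recall 6 or 7 dosing days, depending on whether the form day is counted. It would describe dosing weeks only, could miss effects that appear off drug, and would separate QoL from the 2-monthly clinic and MRI visits.
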